Post-operative infections are a serious cause of complication after surgery. Cesarean sections are unique because by definition they are contaminated by the vagina, as the uterus is contiguous with the vagina anatomically. When a surgical opening is created involving the uterus vaginal bacteria is unavoidably deposited into the abdominal space during delivery of the infant. Methods of procedure and sterile techniques are deployed throughout the procedure to minimize post c-section infections. Women with morbid obesity are at highest risk for development of surgical site infection. At Regions Hospital, post-operative surgical site wound care is addressed with the use of a prophylactic negative pressure wound therapy (NPWT) device (wound vacs) in lieu of traditional bandages after cesarean section in women at high risk for infection (BMI > or = 40). Alternatively many of the OB/GYNs have also started using a competing product called Mepilex Border Post-Op Ag for all patients. CMS (the dominant insurer of pregnant women in the US) has determined other types of pelvic surgery surgical site infections as a hospital acquired condition (HAC), which is tied directly to reimbursement. Though not currently affected by this policy, c-section surgical site infections may be considered in the future. So developing cutting edge practice now may avoid higher surgical site infection rates correlating directly to loss of reimbursable care to the hospital. Eliminating surgical site infections positively affects patient's well-being and the hospital's fiscal health. There is conflicting published data on benefits of surgical site dressing decisions for cesarean section. In our practice we have found it difficult to find a difference, however we have noted that our surgical site bundle (everything we do to prevent infections such as antibiotics, soaps, washes, etc) has dramatically reduced our surgical site infections. Recent studies demonstrate little benefit of the negative pressure wound therapy. However, published research, performed at Regions, and utilizing internal data suggests that negative pressure wound therapy lowers the incidence of surgical site infection rate in cesarean sections. We would like to evaluate the benefits of continuing the negative pressure wound therapy that some of our doctors use against using the Mepilex bandage that many of our other doctors use. It is not common practice to obtain consent prior to placing a bandage and is generally surgeon preference. In performing cesarean sections we currently place these bandages without informed consent (the surgery, is of course performed with informed consent). In our study we will compare the bandages selected based on surgeons' preferences and compare differences in infection rates over a 2 year period of time.

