- Our first of two strategies that our OB/GYNs use relies on negative pressure therapy (wound vacs) in high risk patients. We do not currently use it on obese patients (BMI > or = 30 and < 40), we do use it on patients with morbid obesity (BMI > or = 40). We use standard bandages for patients that are not morbidly obese (BMI <40), which generally is a sterile gauze. Recently our many of the OB/GYNs in our group have decided a more cost effective strategy based on high expenses from the wound vacs based on national trends with OB/GYNs as well as success in Regions Hospital with low post operative wound rates; the use the Mepilex Border Post-Op Ag dressing. The OB/GYNs who have continued with the wound-vac based strategy did not want to switch dressing types and are interested on building on our group's demonstrated improvement. In 2018 about half of our infections were in high-risk patients and half were in low-risk patients. Our infection rate is about 4-10 / 500 =

0.8-2% (annual volume is about 500 cesarean sections); we consider this to be good relative to national averages (5-10%). Our goal is 0%.

- Because post-operative infections are relatively rare the effects of bandages cannot be easily determined without a research protocol to control for confounding variables. In our goal of doing no harm our goal post-operative infection rate is 0%. We would like to systematically approach methods to help us achieve this goal.
- We use surgical site infection prevention bundles to help prevent infections including a preoperative wash, a surgical sterilization/prep, sterile technique, pre-operative antibiotics and sterile abdominal dressing. Our practices change with time and the only way to know the effect of one particular change in this overall uncommon (but clinically salient) complication is to study it; fortunately we are already practicing and collecting data in a way that studying these effects would not affect our patients.
- The negative pressure therapy costs \$300-500 per patient. A standard bandage is <\$4. A silver impregnated silicone post-op dressing costs \$20. This study would help address whether using a silver impregnated silicone foam would be cost effective in all patients or just in the high-risk population. If used universally savings in the high risk group could offset increased costs in the low risk group; costs are generally incurred by the hospital and not billed to the patient.

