- There is only 1 randomized control trial of negative pressure therapy; its limitation is that it is underpowered at about 160 patients in the final pool with 300 in the study. Its findings do not demonstrate a difference in negative pressure therapy however there are limitations in the study – it is underpowered and dressings are not kept on in both treatment groups for the same amount of time, which is a confounding factor. Also the study does not address a strategy for low-risk groups (1). There are no studies on the silver-impregnated bandage for comparison despite being commonly used. Just as benefit has not been clearly demonstrated, harm has also not been demonstrated (or suggested, aside from cost).
- A retrospective study comparing negative pressure therapy in obese women was conducted at Regions Hospital, it demonstrates benefit in this type of dressing in high-risk (BMI > or = 40) patients (2). Meta analyses of several retrospective studies demonstrate heterogeneous but overall beneficial effects of negative pressure therapy versus "standard" dressing, but they are not compared to silver-impregnated bandages such as proposed in the current IRB request.
- Silver has antibiotic properties and has been used anecdotally by several services within our hospital with good effects (including in the principal investigator's prior practice). In other words, using silver impregnated bandages is considered a routine practice in many practices following cesarean section.
- Our study will fill the gap in that it will have more power than previously conducted research in the field. It will also compare a bandage that is thought to have antibiotic properties (the "silver" component of the silver impregnated silicone foam dressing). The silver impregnated silicone foam dressing is significantly less expensive than negative pressure therapy and slightly more expensive than a standard gauze dressing. This study will help us fill the knowledge-gap in whether there are significant differences in 2 arms of our study: negative pressure therapy vs silver impregnated silicone dressings in high risk patients (BMI > or = 40) and also standard gauze dressing vs silver impregnated silicone dressing in normal risk patients (BMI < 40). This will help us find a clinically prudent method to achieve zero surgical site infections while maintaining our fiduciary responsibility to our patients.

4. Approach

a. Study design

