- Study design will be in a prospective cohort trial. The first cohort will be patients who are having a cesarean section with OB/GYNs that prefer using paper bandages in patients with BMI <40 and prophylactic wound vacuum therapy in patients with BMI > or = 40. The second cohort will be patients who are having a cesarean section with OB/GYNs that prefer using Mepilex Border Post-Op Ag regardless of BMI.
- This will be a pilot study as infection rates are low enough that a full study would take several years. However, if difference between methods are large enough then the study would be able to reveal this (see sample size section for details)
- There will be two cohorts:

- 1) Cohort 1 - Normal risk (BMI < 40) – standard dressing (sterile gauze dressing)
High risk (BMI > or = 40) – negative pressure wound therapy / "wound vac"
- 2) Cohort 2 - Normal risk (BMI < 40) – silver impregnated silicone dressing
High risk (BMI > or = 40) – silver impregnated silicone dressing

b. Population

i. Inclusion/Exclusion Criteria [See Human Subjects items to be moved here]

- Inclusion/exclusion criteria: pregnant women who have a cesarean section; as the bandage will be applied when women are no longer pregnant (after fetus is delivered) they will technically not be pregnant at the time of inclusion in the study
- Women will be excluded from the study if their bandage / BMI are not compatible with the cohort scheme noted above (for example if the patient's OB/GYN uses a bandage that is different than a wound vac, paper bandage or Mepilex dressing).
- Specific diagnosis & procedure codes – pregnancy, cesarean section not having other abdominal surgery (example: concomitant hernia repair) except for with concomitant bilateral tubal ligation, which is often done with cesarean sections
- Specific demographic inclusion/exclusion criteria – women of child bearing age having cesarean section at Régions Hospital
- We will compare patients to a database of patients who have asked to be excluded from research, we will exclude patients who requested this. This information is kept in central HealthPartners databases.

ii. Sample size

- Sample size of records to be obtained – enrollment will be 2 years, 1000 women
- Sample size for the main analysis – anticipated follow-up of 75%, which would net 750 women

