Descriptive statistics generally as mean or total; chi-squared, Students t-test, Fisher exact tests as appropriate. Regression may be difficult with low infection rates.

- Anticipate roughly 300-600 participants per cohort (after accounting for patient follow-up)
- Variables per section "E" above
- Silver impregnated silicone dressing versus wound vac/paper dressing will be 1 study analysis. Then stratification by arm will be completed
- Infection rate will be reported as number (proportion). Clinical significance will be $P<0.05$. Dichotomous/categorical data will be reported as a proportion. Continuous variables may be dichotomized versus kept as a scale depending on the analysis (for example in our $BMI > or = 40$ versus $BMI <40$ would be one example of dichotomized data). Hemoglobin a1c (a measure of diabetic control) would likely be dichotomized into <7 (preferred in pregnancy) versus >7 .
- Missing data will be analyzed on a per-participant basis—for example if there is a recent BMI and not one done the day of surgery that may be used. Missing data that is used will be reviewed by a second investigator for appropriateness, if not certain then a third investigator will opine as to the appropriateness as a tie-breaker.
- We will obtain hospital / practice billing data averages (for patient care in general) to multiply by the additional visits (ER, home healthcare or clinic), admissions, procedures and surgeries to increase the clinical salience of our analysis.
- [name] wrote the analysis plan and will complete the analysis plan. SPSS v25 or similar will be used. A statistician from the HealthPartners Institute Research Methodology Group will be used for post hoc analysis for additional insight. [name] is confident he can complete descriptive as well as analytic statistics based on prior studies. He has generally performed his own statistical analysis when performing original research; post hoc statistician analysis has been consistent with his findings in these studies.

f. Power analysis or statement of precision

The following study parameters were used to find an appropriate sample size:

Study Parameters:

Incidence, group 1:	0.5%
Incidence, group 2:	3%
Alpha:	0.05
Beta:	0.2
Power:	0.8

The following sample sizes would be needed to have adequate power with a dichotomous endpoint, two independent sample study:

Sample Size:

Cohort 1	431 (silver impregnated silicone bandage)

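### The overall silver versus wound-vac/gauze comparison is planned only as a crude test: no BMI-adjusted overall estimate is specified, and the limitations omit confounding between the surgeon-chosen cohorts

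*Combined protocol and SAP*

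**What the plan says.** **Allocation.** The Summary (section 1) says "In our study we will compare the bandages selected based on surgeons", and completes the sentence with their preferences. Section 4.a forms the second cohort from women "having a cesarean section with OB/GYNs that prefer using Mepilex Border Post-Op Ag regardless of BMI". The other cohort has surgeons who use gauze below BMI 40 and a wound vac from BMI 40 up.

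**Analysis.** Section 4.e sets the sequence: "Silver impregnated silicone dressing versus wound vac/paper dressing will be 1 study analysis. Then stratification by arm will be completed". The methods listed are "chi-squared, Students t-test, Fisher exact tests as appropriate. Regression may be difficult with low infection rates". No Mantel-Haenszel, standardised, regression or propensity-based overall estimate is named. BMI, to one decimal place, is on the chart-review form in section 4.d.

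**Meaning of arm.** Section 4.e does not define it, but section 3 does. It describes "2 arms of our study: negative pressure therapy vs silver impregnated silicone dressings in high risk patients", and pairs this with gauze versus silver below BMI 40. Two BMI-specific contrasts are therefore planned.

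**Exclusions.** Section 4.b: "Women will be excluded from the study if their bandage / BMI are not compatible with the cohort scheme noted above".

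**Confounding.** Section 3 says that bandage effects "cannot be easily determined without a research protocol to control for confounding variables". Section 6 describes the proposed approach in the same terms. Neither gives a method. Section 4.g discusses sample size, generalisability, false negatives, a patient population at higher risk than in community hospitals, and ascertainment. It does not mention differences between the two cohorts.

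**The concern.** The cohorts are not randomised, so nothing in the design balances them. BMI is the strongest risk factor that the documents put a figure to. Section 3 reports that "In 2018 about half of our infections were in high-risk patients and half were in low-risk patients", and women with BMI ≥40 are presumably a minority. If surgeons who prefer silver see a different share of such women from the other surgeons, the pooled infection rates differ even when the dressings perform identically, and the crude overall test attributes that difference to the dressing.

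The two stratum contrasts avoid confounding by BMI category. The BMI ≥40 stratum is too imprecise to carry a conclusion alone, so the overall result may well be the one that is used. Section 4.f expects the study to be able to inform practice whichever way it comes out, and section 8 foresees changes within weeks of the analysis. That is a reason to specify the overall estimate properly, even in a study described as a pilot and as exploratory.

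**Working it through.** **1. The plan's own sample size.** Section 4.f uses 0.5% versus 3%, alpha 0.05 and power 80%. The crude two-sided two-proportion formula, with mean proportion 0.0175, gives

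n = [1.960·√(2 × 0.0175 × 0.9825) + 0.842·√(0.005 × 0.995 + 0.03 × 0.97)]² / 0.025²
= (0.3635 + 0.1554)² / 0.000625 = 430.7, so 431 per cohort.

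This reproduces the stated figure. The study was sized for the crude overall contrast, with no stratum or covariate term.

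**2. Inputs for the illustration.**
- From the documents: overall infection rate r of 0.8–2% (section 3; 1% and 2% used below); half of infections in BMI ≥40 (section 3); 750 analysable women (section 4.b), so about 375 per cohort.
- Assumed, because the documents do not give them: BMI ≥40 share s of 10, 15 or 20%; a gap g of 5 or 10 points between cohorts, centred on s; no dressing effect.

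**3. Stratum risks.** BMI ≥40: h = 0.5r/s. BMI <40: l = 0.5r/(1 − s). The ratio h/l = (1 − s)/s is 9.0, 5.7 or 4.0.

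**4. Spurious crude difference.** It equals g × (h − l). For r = 1%, s = 10%, g = 10 points: h = 5.00% and l = 0.556%. The crude rates are 0.15 × 5.00 + 0.85 × 0.556 = 1.222% and 0.05 × 5.00 + 0.95 × 0.556 = 0.778%. The difference is 0.44 points and the risk ratio 1.57.

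| s | g | Risk ratio | Difference at 1% (points) | Difference at 2% (points) |
|---|---|---|---|---|
| 10% | 5 | 1.25 | 0.22 | 0.44 |
| 15% | 5 | 1.15 | 0.14 | 0.27 |
| 20% | 5 | 1.10 | 0.09 | 0.19 |
| 10% | 10 | 1.57 | 0.44 | 0.89 |
| 15% | 10 | 1.32 | 0.27 | 0.55 |
| 20% | 10 | 1.21 | 0.19 | 0.38 |

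**5. Size against sampling error.** At 1%, the crude 95% half-width with 375 per cohort is about 1.96 × √(2 × 0.01 × 0.99/375) = 1.42 points. A 10-point gap therefore gives a bias of 13–31% of the half-width (0.19/1.42 to 0.44/1.42).

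**6. False-positive rate.** Simulation with 40,000 runs per setting, a 10-point gap, and Fisher's test when an expected count is below 5 (chi-squared otherwise). For s = 10/15/20%, type I error is 4.5/2.9/2.5% at a 1% rate and 12.7/7.6/5.6% at 2%. With a 5-point gap it is at most 2.5% and 6.5% respectively.

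**7. Performance of the alternative.** The difference standardised to the combined BMI distribution averages within about 0.01 points of zero in the no-effect settings. Its standard deviation is at most about 8% larger than the crude one. With opposite stratum effects the increase reaches 13.5%.

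**8. Stratum precision.** With 2 versus 2 infections, Newcombe 95% half-widths are 6.8–12.6 points for BMI ≥40 (75 down to 38 women per cohort) and 1.6–1.8 points for BMI <40 (337 down to 300).

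**9. Exclusion rule.** Silver fits the scheme at any BMI, so a BMI mismatch can remove only women given gauze or a wound vac. If fractions d (BMI ≥40, given gauze) and e (BMI <40, given a wound vac) are removed, the share left is s(1 − d)/[s(1 − d) + (1 − s)(1 − e)]. At s = 20%: d = 30%, e = 0 gives 14.9%; d = 0, e = 10% gives 0.20/0.92 = 21.7%; d = e gives no shift. The direction is therefore unknown.

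**The case against.** The strongest reply is that BMI is the one confounder the plan already handles. Read with section 3, stratification by arm delivers both BMI-specific contrasts. A reader might infer that the plan ignores BMI or leaves arm without meaning, but the combined document does not support that. What stands is narrower: there is no adjusted overall estimate.

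Second, the premise is assumed. No section gives the BMI ≥40 share or suggests that it differs by surgeon. The 50/50 split rests on one year with perhaps 4–10 infections. For 5 of 10, the exact 95% limits are 19–81%, which at a 10% share imply a BMI risk ratio anywhere from about 2 to 39. Those infections may also reflect dressings that already differed by BMI. This stands, so the table is an illustration and not a forecast.

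Third, a reader might infer that the crude test has a generally inflated false-positive rate. The simulation does not support that: there is no inflation at 1%, and it is material mainly for a 5% versus 15% split at a 2% rate. The harm is chiefly to the point estimate.

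Fourth, a reader might infer that the exclusion rule tilts the cohorts in a known direction. It acts on one cohort only, but gauze at BMI ≥40 and a wound vac below 40 shift the mix in opposite directions, and neither frequency is given.

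The plan's remark that regression may be difficult is fair: 750 women at 0.8–2% yield about 6–15 infections. That limits a multivariable outcome model. It does not rule out a weighted difference over two strata.

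**Conclusion.** The point holds, at minor to modest severity. The overall contrast between surgeon-chosen cohorts is specified only as a crude test. BMI is collected, but no BMI-adjusted overall estimate is planned. Confounding between cohorts is missing from section 4.g, while sections 3 and 6 imply that it is controlled.

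The possible bias is a risk ratio of 1.10–1.25 for a 5-point gap and 1.21–1.57 for a 10-point gap. It depends wholly on the assumed shares and gaps and on the imprecise half-and-half split, and it is nil with equal BMI mixes. BMI adjustment would not make the comparison unconfounded: surgeon is tied to dressing, and the listed form has no surgeon field.

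**What to change.** 1. In section 4.e, lead the overall contrast with the risk difference standardised to the BMI distribution of all analysed women: w × (difference in BMI ≥40) + (1 − w) × (difference in BMI <40), where w is the BMI ≥40 share of both cohorts combined. Name one 95% CI method suited to sparse events. Take the significance decision from that same estimate and interval, and keep the crude test as descriptive. A separate Mantel-Haenszel test should not supply the decision: in simulation it disagreed with the standardised interval on significance in 5.4% of runs under no effect and in 10.2% with opposite stratum effects.
2. Report the two planned BMI-stratum differences with Newcombe score-based 95% CIs.
3. Add to section 4.g that confounding by surgeon and case mix remains, and soften the confounding-control wording in sections 3 and 6.

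**Cost.** SAP wording and a few hours of analysis. BMI and cohort are already on the form, so no new data are needed. The text should be settled before analysis, since section 4.e brings in the statistician only post hoc. The interval may be up to about 8% wider under no effect, or 13.5% with opposite stratum effects. Surgeon effects and risk differences within BMI strata are not removed.

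**Optional.** A baseline table by cohort; a propensity-weighted sensitivity analysis, which may be unstable with so few infections; and counts of mismatch exclusions by dressing and BMI group. The counts would need dressing type abstracted from operating room records, because the form codes only cohort 1 or 2.
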